7.8.2 Analysis of Secondary Efficacy Endpoint

For the secondary endpoint, percent change from baseline in PVR at Visit 4, the same approach as in the primary analysis will be used.

Composite clinical endpoints at 6 months after PEA will be tabulated by treatment group containing the number and percentage of patients with an event as well as the number of event. The Fisher exact test will be utilised to test the proportion difference along with the Clopper-Pearson exact CI when applicable. For analysis based on the ordinal response of functional class, the row mean score from the Cochran-Mantel-Haenszel test will be used to test the response difference between groups.

Circulatory arrest time from perioperative findings will be tabulated by treatment group using the descriptive statistics. An analysis of variance may be employed to compare the mean difference between 2 groups. In case normality assumption cannot hold, the Wilcoxon rank-sum test should be considered.

Surgery-related complications from the perioperative findings will be tabulated by treatment group in a descriptive way, presenting the number and percentage of patients for each symptom.

For surgical evaluation of specimen endpoints, ease of dissection plane and completeness of disease clearance will be tabulated by treatment group containing the number and percentage of patients in each level. The Cochran-Mantel-Haenszel test will be used to test the ordinal response difference between groups if deemed necessary.

Clot and vessel wall friability, measured as more solid than usual, normal, or more friable than usual, will be tabulated by treatment group containing the number and percentage of

patients in each level. The Cochran-Mantel-Haenszel test will be used to test the ordinal response difference between groups if deemed necessary.

All-cause death during the whole study course and withdrawal during the randomised treatment phase will be tabulated by treatment group containing the number and percentage of patients with event. Time to death will be analysed using the Kaplan-Meier method.

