4.2. Randomisation, Stratification, and Blinding

Following completion of the screening period, eligible study patients will be randomly assigned into the study. An interactive web response system (IWRS) will be used to administer the randomisation schedule. In order to obtain a treatment group assignment for a patient, a site representative will access the IWRS. Patients will be randomly assigned on Day 1 to receive

either riociguat or matching placebo tid in a 1:1 allocation ratio for 3 months. No stratification of the randomisation schedule will be performed.

The clinical study will be performed in a double-blinded manner. The investigator, study coordinator(s), patients, and the sponsor study team and its representatives will be blinded to the identity of the randomised treatment assignment from the time of randomisation until database lock. Randomisation data will be kept in strict confidence by the statistician who will generate the randomisation schedule, the IWRS provider, and the vendor involved in the study drug labelling. The identity of the treatments will be concealed by the use of study drugs that are all identical in packaging, labelling, schedule of administration, appearance, taste, and odour.

A patient's treatment assignment will not be broken until the end of the study unless medical treatment of the patient depends on knowing the study drug the patient received. In the event that the blind needs to be broken because of a medical emergency, the investigator may unblind an individual patient's treatment allocation. As soon as possible, the investigator should first contact the medical monitor to discuss the medical emergency and the reason for revealing the actual treatment received by that patient. The treatment assignment will be unblinded through IWRS. Reasons for treatment unblinding must be clearly explained and justified in the eCRF. The date on which the code was broken together with the identity of the person responsible must also be documented.

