8.2.2. Composite Clinical Endpoints

Composite clinical endpoints from randomisation to Visit 4 will be tabulated by treatment group containing the number and percentage of patients with an event as well as the number of event for the PEA set and the PPS. The Fisher exact test will be utilised to test the proportion difference along with the Clopper-Pearson exact CI when applicable. For analysis based on the ordinal response of functional class, the row mean score from the Cochran Mantel-Haenszel test will be used to test the response difference between groups.

Composite clinical endpoints include following clinical endpoints:

- All-cause death

All deaths that happen after randomisation until the date of Visit 4, 6 months after the PEA, will be included.

- PH-related hospitalisation

All PH-related hospitalisation except the in-hospital care after PEA from randomisation until 6 months after PEA will be included.

- Need for PAH-targeted therapy

All PAH-targeted therapy from randomisation until 6 months after PEA will be included.

- Functional class unchanged or worse

When comparing the functional class assessment at Visit 1 with the functional class assessment at other visits, the same class will be defined as unchanged, and a higher class will be defined as worse. The worst case after treatment will be used.

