8.3. Exploratory Efficacy Endpoints

Exploratory efficacy endpoints are defined in Section 3.2.3. No formal assessment of difference between treatment groups will be performed for any of the exploratory efficacy endpoints. The difference between treatment groups in exploratory efficacy endpoints will be estimated with 95% CIs to quantify the treatment effect.

Summary tables presenting observed values and changes from baseline for NT-proBNP measurement concentration (pg/mL), cardiac output (L/min), cardiac index (L/min/m²), mRAP (mmHg), mPAP (mmHg), and PAWP (mmHg) will be provided for each treatment group by scheduled visits using descriptive statistics. The difference in the change from baseline between treatment groups with 95% CIs will be estimated non-parametrically using Hodges-Lehmann estimation of location shift in the tables. The analyses will be based on the PEA set and the PPS.

Hospital length of stay in days and ICU length of stay in days will be summarised using descriptive statistics. The difference between treatment groups with 95% CI will be estimated non-parametrically using Hodges-Lehmann estimation of location shift in the table. The analyses will be based on the PEA set.

Time from start of ICU stay to end of mechanical ventilation (in hours) will be analysed using the Kaplan Meier method. Median and quartiles in days and associated 95% CI will be calculated using the LOGLOG transformation. All patients stayed in ICU who do not have end date of mechanical ventilation will be censored at the time of discharged from the ICU. The analyses will be based on the PEA set.

Proportion of in-hospital mortality will be summarised using the frequency counts and percentages for the PEA set. Proportion difference between treatment groups along with the Clopper-Pearson exact CI will be provided

The proportion of patients who need PAH-targeted therapy immediately after PEA to Visit 4 will be summarised using the frequency counts and percentages for the PEA set and the PPS. Proportion difference between treatment groups along with the Clopper-Pearson exact CI will be provided.

WHO functional class will be summarised by scheduled visit for each treatment group. Shift table of baseline functional class versus functional class at each postbaseline scheduled visit will be provided. The analyses will be based on the PEA set and the PPS.

9. Safety Analysis

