13.1. Schedule of Events

	Visit 0 Pretreatment / Screening	Visit 1 Randomisation & baseline visit	Visit 2 RHC visit (Pre- PEA)	Visit 3 Post-PEA	Visit 4 Follow-up visit incl. RHC
Time frame	Day -89 to 1	Day 1	Day 90+30	Day 96 ^a	Day 276±10
Activity / Observation					
Written informed consent	X				
Inclusion/exclusion criteria review	X	(X) ^b			
Assessment of current tobacco use	X				
Demographic data including height and weight	X				
HIV test	(X) ^b	X			
Medical and treatment history	X	X			
Physical examination including WHO functional class	X	X	X	X	X
Vital sign measurements	X	X	X	X	X
Clinical laboratory assessments (haematology, clinical chemistry, and urinalysis)	(X) ^b	X	X	X	X
NT-proBNP measurement		X	X		X
Haemodynamics incl. PVR, mRAP, mPAP, cardiac index, pulmonary artery wedge pressure measurement	X ^c		X		X
12-lead ECG		X	X		X
Pregnancy test (if applicable) ^d	X	X	X		X
Randomisation/treatment assignment		X			
Administration of double-blind study drugs ^e		X	X		
Provision of patient diary	X				

	Visit 0 Pretreatment / Screening	Visit 1 Randomisation & baseline visit	Visit 2 RHC visit (Pre- PEA)	Visit 3 Post-PEA	Visit 4 Follow-up visit incl. RHC
Time frame	Day -89 to 1	Day 1	Day 90+30	Day 96 ^a	Day 276±10
Activity / Observation					
Perioperative assessment (circulatory arrest time, surgery-related complications)			X ^f		
Surgical evaluation of specimen ^g				X ^g	
Hospital and ICU length of stay				X	
Time on mechanical ventilation				X	
PAH-targeted therapy assessment	X	X	X	X	X
PH-related hospitalisation		X	X	X	X
Adverse event monitoring	X	X	X	X	X
Concomitant medications		X	X	X	X
Return of patient diary				X	
Return of study drug				X	
Telephone call			X ^h		X ⁱ
Patient compliance check (study procedures and study drug)		X	X	X	X

Abbreviations: ECG, electrocardiogram; HIV, human immunodeficiency virus; ICU, intensive care unit; incl., including; mPAP, mean pulmonary arterial pressure; mRAP, mean right atrial pressure; NT-proBNP, N-terminal pro-B-type natriuretic peptide; PAH, pulmonary arterial hypertension; PEA, pulmonary endarterectomy; PH, pulmonary hypertension; PVR, pulmonary vascular resistance; RHC, right heart catheterisation; WHO, World Health Organization

^a The PEA will be conducted by the principal surgeon of the site within a week of RHC.

^b When laboratory analysis results are required/available (see Protocol Section 4.2)

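### The functional-class test in SAP 8.2.2 does not condition on Visit 1 class; it is valid but loses precision, and its response variable is not stated

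*SAP*

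**What the plan says.** SAP 8.2.2 (Composite Clinical Endpoints) tests the ordinal functional-class response as follows: "the row mean score from the Cochran Mantel-Haenszel test will be used to test the response difference between groups". Protocol 7.8.2 gives the same test: "For analysis based on the ordinal response of functional class, the row mean score from the Cochran-Mantel-Haenszel test will be used". Neither names a stratification variable or covariate for it.

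SAP 8.2.2 defines the functional-class component of the composite relative to baseline: "When comparing the functional class assessment at Visit 1 with the functional class assessment at other visits, the same class will be defined as unchanged". Any rise in class counts as worse. For the post-baseline value, "The worst case after treatment will be used".

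The baseline value is available. The row "Physical examination including WHO functional class" in SAP 13.1 is marked at Visits 0 to 4. SAP 8.3 uses it descriptively: "Shift table of baseline functional class versus functional class at each postbaseline scheduled visit will be provided". On allocation, SAP 4.2 says: "No stratification of the randomisation schedule will be performed". Protocol 7.8 leaves covariates to the SAP, which names a baseline covariate only for the supportive ANCOVA of PVR (SAP 8.1).

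**The concern.** Class at follow-up is likely to depend on class at entry. The room to change certainly does: a class I patient cannot improve and a class IV patient cannot worsen. The Cochran-Mantel-Haenszel (CMH) statistic is built to take strata, yet none is given.

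Two things follow. Variation that baseline class could explain stays in the variance of the statistic. And with about 40 patients per arm and no stratified randomisation, the arms can differ noticeably in baseline class by chance, with nothing in the test to take that out. A stratum added after unblinding, once an imbalance had been seen, would be post hoc. The SAP is to be finalised before database lock and unblinding (SAP 1), so that is the time to name it.

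**Working it through.** **Inputs from the documents.** 88 randomised 1:1 with 10% dropout (SAP 4.1); target of 80 completers (Protocol 4.3.3); two-sided 5% level without multiplicity adjustment (SAP 4). The plan's only related figure reproduces: 80 × 1.10 = 88 (80 / 0.90 = 88.9 would give 89). So 44 per arm are randomised and about 40 complete. No power is stated for this test, so there is none to reproduce.

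**Assumptions, not in the documents.** Baseline classes I to IV at 3/27/60/10%. Two control-arm follow-up distributions: A = 35/45/17/3% and B = 8/37/47/8%. Latent shift 0.5 SD. Latent correlation ρ between baseline and follow-up from 0 to 0.7. One follow-up class per patient.

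**Statistic.** With integer scores y in stratum h, where n_h patients include n_1h on riociguat and n_0h on placebo:

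U = Σ_h [ Σ_riociguat y − n_1h·ȳ_h ], V = Σ_h [ n_1h·n_0h / (n_h(n_h − 1)) ]·Σ(y − ȳ_h)², Q = U²/V, compared with 3.84.

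The unstratified test is the case of one stratum.

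**Why conditioning helps.** On the latent scale the residual variance is multiplied by 1 − ρ²: 0.91, 0.75 and 0.51 at ρ = 0.3, 0.5 and 0.7. Four coarse classes recover part of that.

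**Power, 40 per arm, 8000 simulated trials per setting (unstratified → stratified by Visit 1 class).**

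| ρ | Raw class, A | Raw class, B | Change category, A | Change category, B |
|---|---|---|---|---|
| 0 | 49.4 → 48.1% | 53.1 → 51.3% | 24.0 → 31.8% | 29.6 → 42.4% |
| 0.3 | 49.9 → 50.5% | 52.5 → 53.3% | 30.0 → 35.2% | 37.5 → 46.8% |
| 0.5 | 49.5 → 55.2% | 52.9 → 59.4% | 33.3 → 37.4% | 46.9 → 54.2% |
| 0.7 | 48.7 → 63.0% | 52.7 → 67.4% | 39.0 → 42.8% | 60.4 → 64.0% |

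For ρ from 0.3 to 0.7 the gain is about 1 to 15 points on raw class and about 4 to 9 on the change category. With a shift of 0.6 SD the gains are 1 to 15 and 3 to 10. Type I error is 4.4 to 5.3% for all four tests.

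**Chance imbalance.** With 70% in class III or IV (60 + 10), the standard error of the difference between arms is √(2 × 0.7 × 0.3 / 40) = 0.102. A gap of at least 15 points is 6 patients in 40. With continuity correction, z = (5.5/40)/0.102 = 1.34, so the probability is about 18%; the simulation gives 17 to 19%.

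Within those trials, at ρ = 0.3, 0.5 and 0.7, type I error of the unstratified raw-class test is 5–6%, 8% and 11–12%. For the unstratified change category it is 6 to 9%. With strata it is 4 to 6% for both responses.

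The direction depends on the response. If riociguat draws the sicker patients, unstratified raw-class power falls to 35–38%, 27–28% and 18–20% (stratified: 49–51%, 55–58% and 61–65%). On the change category the same imbalance raises the rejection rate, to between 50 and 77% unstratified against 33 to 61% stratified, because sicker patients have more room to improve.

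**Sparse strata.** The assumed split of 80 patients gives 2.4, 21.6, 48 and 8 in classes I to IV. Pooling to I/II v III/IV at ρ = 0.7 gives raw-class power of 56.6% (A) and 63.1% (B), compared with 63.0% and 67.4% for four strata. For the change category under A, pooling leaves 39.6% against 39.0% unstratified, so nearly all of that gain goes.

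**The case against.** A reader might infer that the test ignores baseline class. The documents do not establish that. SAP 8.2.2 defines the component by comparison with Visit 1, and if the tested response is improved/unchanged/worse, baseline is already in it. Only the raw-class reading makes the test blind to baseline, and neither document chooses between the two. This objection stands, but the remedy survives it, because the scope for change still depends on the starting class and stratifying gains power on either reading.

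A reader might also infer that imbalance biases the result or makes the test invalid. It does not: over all randomisations the error rate is about 5%, and chance imbalance is part of the null distribution. The elevated rates above apply only to trials in which a large imbalance has occurred.

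It can fairly be said, too, that every driver of the power figures is assumed. A potentially curative operation lies between Visit 1 and Visit 4, so the correlation could be low, and at 0.3 the raw-class gain is within simulation error. Nor do the simulations model the worst-case selection over visits.

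Finally, Protocol 7 calls all analyses exploratory, the sample size is not based on power, and the composite itself is tested by the Fisher exact test. An unstratified test is defensible in that setting. These points limit the weight of the concern but do not remove it.

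**Conclusion.** The point holds as one of precision and specification. The row-mean-score test in SAP 8.2.2 and Protocol 7.8.2 does not condition on a recorded baseline value that is likely to be prognostic, and its response and visit are undefined. The test remains valid.

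Stratifying would gain roughly 1 to 15 points of power on raw class or 4 to 9 on the change category, under the assumed class distributions, 40 per arm, a 0.5 SD shift and correlations of 0.3 to 0.7. If baseline class does not predict outcome, it costs 1 to 2 points on raw class. It would also protect the realised comparison in the roughly one trial in six (about 18%) with a 15-point baseline gap.

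The documents supply none of the class distribution, effect or correlation, so these figures indicate scale only. The error rates assume a randomised comparison; the analysis uses the PEA set and PPS, which are defined after randomisation. That is a separate matter. Weight: minor to moderate.

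**What to change.** In SAP 8.2.2, before unblinding:

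1. Stratify the row-mean-score test by Visit 1 functional class.
2. Fix the pooling rule in advance. For example, pool to I/II v III/IV if any class has fewer than a stated number of patients per arm. A threshold on both arms combined could be applied at the blind data review.
3. State in the same line whether the response is the class or the change category, and at which visit (or the worst post-baseline value).
4. Name the stratified test as the main one and keep the unstratified test as supportive, so that the choice between two p-values is not left open.

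The cost is one line in the SAP, one more variable in the SAS call, and an entry in SAP 11, since Protocol 7.8.2 gives the test without strata. No new data are needed. The downside is the 1 to 2 points of raw-class power lost if baseline class carries no information, and the loss of part of the gain when strata are pooled.

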4.1.1 Inclusion Criteria

Each patient must meet all of the following criteria to be enrolled in this study:

1. Is a male or nonpregnant and nonlactating female patient aged from 18 to 80 years, both inclusive
2. Is diagnosed with operable CTEPH and anticipating symptomatic and/or prognostic benefit from PEA
3. Has PVR >800 dyn·s·cm⁻⁵
4. Has undergone RHC not more than 180 days before Visit 1
5. Has been treated with anticoagulants for at least 90 days before Visit 1
6. Has ability to swallow oral medication
7. Has ability and willingness to participate and access to the health facility
8. Is capable of understanding the written informed consent and provides signed and witnessed written informed consent
9. Female patient must be either surgically sterile, postmenopausal (no menses for the previous 12 months), or must be practicing an effective method of birth control as determined by the investigator (eg, oral contraceptives, double barrier methods, hormonal injectable or implanted contraceptives, tubal ligation, or male partner with vasectomy or complete abstinence)

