7.2 Secondary Efficacy Endpoints

The secondary efficacy endpoints for the study are mentioned below.

1. PVR (6 months after PEA): percent change from baseline in PVR at Visit 4.

PVR assessment at Visit 4 will use the nominal visit information collected in eCRF without considering the time window because PVR status is expected to be stable after PEA.
2. Composite clinical endpoints (6 months after PEA), including patients with any one of the following clinical endpoints, from immediately after PEA to Visit 4.
 - All-cause death

All deaths that happen after randomisation until the date of Visit 4, 6 months after the PEA, will be included.
 - PH-related hospitalisation

All PH-related hospitalisation except the in-hospital care after PEA from randomisation until 6 months after PEA will be included.

- Need for PAH-targeted therapy

All PAH-targeted therapy from randomisation until 6 months after PEA will be included.

- Functional class unchanged or worse

When comparing the functional class assessment at Visit 1 with the functional class assessment at other visits, the same class will be defined as unchanged, and a higher class will be defined as worse. The worst case after treatment will be used.

3. Perioperative findings at Visit 2:

- Circulatory arrest time
- Surgery-related complications (Section 6.2.7)

4. Surgical evaluation of specimen (difficulty to withdraw obstructive material):

- Ease of dissection plane, classed as easier than normal (1), normal (2), more difficult than normal (3)
- Completeness of disease clearance, classed as better than expected (1), as expected (2), worse than expected (3)
- Both clot and vessel wall will be measured as score of 1 to 3 with the following scores: more solid than usual (1), normal (2) more friable than usual (3).

Surgical evaluations of specimen are from perioperative measures. The data will be treated as an ordinal response. A higher score means a worse case.

5. All-cause death

All deaths that happen during the whole course of the study will be included.

6. Withdrawal during randomised treatment phase

Only withdrawals after randomisation but before PEA will be included.

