3.2.2. Secondary Efficacy Endpoints

The secondary efficacy endpoints for the study are mentioned below.

1. PVR (6 months after PEA): percent change from baseline in PVR at Visit 4.
2. Composite clinical endpoints (6 months after PEA), including patients with any one of the following clinical endpoints, from randomisation to Visit 4.
 - All-cause death
 - PH-related hospitalisation
 - Need for PAH-targeted therapy
 - Functional class unchanged or worse
3. Perioperative findings at Visit 2:

- Circulatory arrest time
- Surgery-related complications (Appendix 13.3)

4. Surgical evaluation of specimen (difficulty to withdraw obstructive material):
 - Ease of dissection plane
 - Completeness of disease clearance
 - Clot and vessel wall
5. All-cause death
6. Withdrawal during randomised treatment phase

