13.2. World Health Organization Classification for Patients With Pulmonary Arterial Hypertension

Functional Class	Symptomatic Profile
I	Patients with pulmonary hypertension but without resulting limitation of physical activity. Ordinary physical activity does not cause dyspnoea or fatigue, chest pain, or near syncope
II	Patients with pulmonary hypertension resulting in slight limitation of physical activity. They are comfortable at rest. Ordinary physical activity causes undue dyspnoea or fatigue, chest pain, or near syncope
III	Patients with pulmonary hypertension resulting in marked limitation of physical activity. They are comfortable at rest. Less than ordinary activity causes undue dyspnoea or fatigue, chest pain, or near syncope
IV	Patients with pulmonary hypertension with inability to carry out any physical activity without symptoms. These patients manifest signs of right heart failure. Dyspnoea and/or fatigue may even be present at rest. Discomfort is increased by any physical activity

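### The composite scores an unchanged WHO functional class as an event with no exception for class I, so a class I entrant with any later class assessment is an event whatever happens (a minor rule error)

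*SAP*

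**What the plan says.** SAP 3.2.2 defines the composite as "including patients with any one of the following clinical endpoints, from randomisation to Visit 4". One of its four components is "Functional class unchanged or worse". SAP 8.2.2 compares each later assessment with Visit 1 and states that "the same class will be defined as unchanged, and a higher class will be defined as worse". The next sentence is "The worst case after treatment will be used". Protocol 7.2 has the same two sentences: "the same class will be defined as unchanged, and a higher class will be defined as worse. The worst case after treatment will be used".

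The scale in SAP 13.2 and Protocol Appendix 2 runs from I to IV. Class I reads "Patients with pulmonary hypertension but without resulting limitation of physical activity", and there is no class below it. The schedule in SAP 13.1 lists "Physical examination including WHO functional class" at Visits 0 to 4, so three assessments follow the start of treatment: Visits 2, 3 and 4.

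None of the 9 inclusion or 20 exclusion criteria in Protocol 4.1 mentions functional class. Inclusion criterion 2 is "Is diagnosed with operable CTEPH and anticipating symptomatic and/or prognostic benefit from PEA", so expected prognostic benefit is enough without symptomatic benefit. SAP Section 11 changes the composite's observation period and analysis sets but makes no exception for class I.

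**The concern.** For a patient in class II, III or IV, no change after surgery can reasonably count as lack of benefit. For a patient in class I it is the best result the scale allows. The rule does not separate the two. A class I patient who stays in class I, survives, needs no PAH drug and has no PH-related admission falls in the same category as a patient who died.

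That event is fixed by the baseline class and says nothing about treatment. Each such patient raises the event rate of the arm they are in and, across both arms, pulls the difference towards zero. Randomisation is not stratified (SAP 4.2), so a few such patients could also fall unevenly by chance.

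**Working it through.** The documents state no event rate, effect size or class distribution for the composite, so there is no figure of the plan's to reproduce. The check has two parts.

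**1. Does the rule force the event?** Take every combination of classes at Visits 2, 3 and 4, which is 4 × 4 × 4 = 64 paths. Under the worst-case sentence, a path is an event if the highest class on it is at or above the Visit 1 class. A path is a non-event only if all three assessments are below the Visit 1 class.

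| Visit 1 class | Non-event paths | Event paths, worst case | Event outcomes, Visit 4 only |
|---|---|---|---|
| I | 0 | 64 of 64 | 4 of 4 |
| II | 1 × 1 × 1 = 1 | 63 of 64 | 3 of 4 |
| III | 2 × 2 × 2 = 8 | 56 of 64 | 2 of 4 |
| IV | 3 × 3 × 3 = 27 | 37 of 64 | 1 of 4 |

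These are counts of possible paths, not probabilities. For class I the event is forced under the worst-case sentence and also if Visit 4 alone is used, so changing the visit rule alone would not remove it. A class I patient who dies before any later assessment is an event through the death component.

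**2. How much could it matter?** Inputs:

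- 40 patients per arm: half of the 80 completers targeted in Protocol 4.3.3, used as an approximation to the analysed number.
- Two-sided Fisher exact test at 5%: SAP 8.2.2 and SAP Section 4.
- Composite rates p of 45% and 20% among patients above class I: **assumed**.
- Share q in class I at Visit 1, equal in both arms: **assumed**, 0 to 10%.

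The rate in an arm is q + (1-q)p. The difference is therefore (1-q) × (0.45 - 0.20).

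| q | Arm rates | Difference (points) | Exact Fisher power |
|---|---|---|---|
| 0 | 45.0% v 20.0% | 25.0 | 0.59 |
| 2.5% (1 per arm) | 46.4% v 22.0% | 24.4 | 0.55 |
| 5% (2 per arm) | 47.8% v 24.0% | 23.8 | 0.52 |
| 10% (4 per arm) | 50.5% v 28.0% | 22.5 | 0.46 |

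For example, at q = 10% the rates are 0.10 + 0.90 × 0.45 = 0.505 and 0.10 + 0.90 × 0.20 = 0.280. With assumed rates of 50% v 20% the pattern is the same: the difference goes from 30.0 to 27.0 points and power from 0.75 to 0.63 at q = 10%.

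One class I patient can move an arm's rate by at most 1/40 = 2.5 points. The expected shift is (1-p)/40, which is 0.55/40 = 1.4 points at 45% and 0.80/40 = 2.0 points at 20%.

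**The case against.** The strongest reply is that the case may never arise. Patients enter with PVR above 800. Criterion 2 permits a patient without expected symptomatic benefit, but it does not show that any class I patient is expected. If none enrols, no result changes. This stands, and it limits the size of the point but not its correctness.

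The effect is also small beside sampling error. At 45% v 20% with 40 per arm, the approximate 95% half-width is 1.96 × √(0.45 × 0.55/40 + 0.20 × 0.80/40) = 19.8 points, against a loss of 0.6 points for one class I patient per arm. The composite is secondary, Protocol Section 7 calls all analyses exploratory, and the sample size is not based on power. The shift table of functional class in SAP 8.3 would show any patient who stayed in class I. All of this stands, although the shift table does not correct the composite count.

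A reader might infer more than the text supports in four ways:

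- **That the rule works for the other classes, with III to II or II to I simply a non-event.** Because the worst case is used, these are non-events only if the patient is better than the Visit 1 class at every post-treatment assessment. The visit rule probably has the larger numerical effect.
- **That the rule favours one arm.** With an equal share in each arm it dilutes the difference. Any imbalance would come from chance.
- **That every class I entrant is an event without condition.** A surviving patient with no later class assessment and no other component event is not covered, because no missing-data rule is given for this component.
- **That exempting unchanged class I is a full repair.** Under the worst-case sentence, a class I patient recorded in class II at Visit 2 or 3 and back in class I at Visit 4 would still be an event.

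**Conclusion.** Wrong as written, minor. That a patient in class I at Visit 1 with any later class assessment is an event follows from the text alone and needs no assumption: all 64 paths are events, as are all 4 outcomes at Visit 4.

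The size rests wholly on assumptions. If q is between 2.5% and 10% and the other patients' rates are 45% v 20%, the difference loses 0.6 to 2.5 points and Fisher power drops by 0.04 to 0.13. If q is zero, nothing is lost. The documents do not support a claim that class I entrants will be more than rare. The primary endpoint is unaffected.

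**What to change.** In SAP 8.2.2, define the component as functional class worse than at Visit 1, or unchanged in a patient who was in class II, III or IV at Visit 1. Remaining in class I is then not an event.

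In the same paragraph, name the visit at which the comparison is made, for example Visit 4, in place of the worst-case sentence, so that a temporary rise at Visit 2 or 3 does not by itself make the patient an event. State also how a survivor without a class at that visit is counted.

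Record the change in SAP Section 11, since it departs from Protocol 7.2, and make it before the blind is broken. The cost is a few lines of text, with no new visit or data. The class I clause changes nothing if no class I patient enrols. Naming the visit is the wider change, because it also affects how patients in classes II to IV are counted.
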